CPU	Clinical Pharmacology Unit
CRO	Clinical Research Organization
CSR	Clinical Study Report
CV	Coefficient of variation
CVID	Common variable immunodeficiency
DBP	Diastolic blood pressure
ECG	Electrocardiogram
FDA	Food and Drug Administration
Fe	Percentage of drug excreted unchanged in the urine
FIH	First-in-human
FSH	Follicle stimulating hormone
GCP	Good Clinical Practice
GD IgA	Galactose deficient IgA (synonymous with a-g IgA)
GLP	Good Laboratory Practice
GMR	Geometric Mean Ratio
hCG	Human Chorionic Gonadotropin
HIPAA	Health Insurance Portability and Accountability Act

HIV	Human Immunodeficiency Virus
HBsAg	Hepatitis B surface antigen
IB	Investigator's Brochure
ICD	Informed consent document
ICH	International Council for Harmonisation
IEC	Independent Ethics Committee
Ig	Immunoglobulin
IgAN	IgA nephropathy
IgG ₂	Immunoglobulin G
IMP	Investigational medicinal product
IND	Investigational New Drug
IRB	Institutional Review Board
KLH	Keyhole limpet hemocyanin
mAb	Monoclonal Antibody
MedDRA	Medical Dictionary for Regulatory Activities
MID	Minimum Intolerable Dose
MTD	Maximum tolerated dose
NOAEL	No observed adverse effect level
OTC	Over-the-counter
PD	Pharmacodynamics
PK	Pharmacokinetics
PT	Preferred Term
QTcB	QT interval corrected for heart rate using Bazett's correction
QTcF	QT interval corrected for heart rate using Fridericia's correction
RR	Respiratory rate
SAE	Serious adverse event
SBP	Systolic blood pressure
SID	Subject identification
SMC	Safety Monitoring Committee
SOC	System Organ Class
SOP	Standard operating procedure
TACI	Transmembrane activator and CAML interactor
t _½	Terminal elimination half-life

T _{max}	Time of maximum serum concentration
US	United States
ULN	Upper level of normal
Vd	Apparent volume of distribution
WBC	White Blood Cells
WHO	World Health Organization

1. INTRODUCTION

1.1. Background

VIS649 is a humanized immunoglobulin G (IgG₂) monoclonal antibody that binds to and blocks the biological actions of the B-cell growth factor, APRIL (A Proliferation Inducing Ligand), preventing binding to its receptors, transmembrane activator and CAML interactor (TACI) and B-cell maturation antigen (BCMA). Through these receptor interactions, APRIL regulates B-cell-mediated immune responses through several mechanisms, including the induction of class switch recombination as well as promotion of plasma cell survival.

VIS649 binds human APRIL with picomolar affinity/avidity as measured by antigen-binding enzyme-linked immunosorbent assay using recombinant trimeric APRIL. VIS649 blocks recombinant APRIL-APRIL receptor interactions, thereby inhibiting APRIL-mediated signaling and B cell proliferation. VIS649 also binds cynomolgus monkey APRIL, with similar affinity and inhibition of APRIL mediated signaling in both species. The physiological and toxicological effects of VIS649 were therefore evaluated in cynomolgus monkeys, in three pre-clinical studies.

In an initial non- Good Laboratory Practice (non-GLP) *in-vivo* toxicology study, weekly administration of IV VIS649 at a dose of 25 mg/kg for 8 weeks resulted in an approximately 70% reduction in serum IgA levels (in comparison with control animals) with minimal effect on serum IgM, and an approximately 40% reduction in serum IgG levels. Hematology assessment did not reveal significant perturbation in white blood cell (WBC), lymphocyte, or leukocyte counts and there were no significant differences between treatment groups noted in the peripheral blood and tissue immune profiling, which included markers for total T cells, helper T cells, cytotoxic T cells, natural killer cells, and B cells. In a subsequent, non-GLP dose range-finding study, VIS649 was

administered weekly over 4 weeks to groups of cynomolgus monkeys at doses of 0 (control), 0.5, 2.5, and 10 mg/kg, with an 8-week recovery observation period. Following treatment with 0.5 and 2.5 mg/kg doses, there was a [REDACTED] reduction from baseline in serum IgA levels. Monkeys treated with 10 mg/kg doses had a [REDACTED] reduction in serum IgA levels, similar to the effect observed in the prior study with 25 mg/kg dosing for 8 weeks, and thus providing evidence that APRIL inhibition does not completely suppress IgA production. Serum IgA level suppression was reversible, with a dose response in time-to-recovery during the 8-week follow-up period. The observation of a maximal suppressive effect of VIS649 on serum IgA levels [REDACTED] in monkeys was further supported in the third toxicology study, described below. There was a lesser effect of VIS649 on serum IgG levels [REDACTED] and IgM levels were not altered notably, in comparison with control animals. Peripheral blood lymphocyte counts were not significantly affected, including the following cell populations: T-lymphocytes (including T-helper and cytotoxic T-cell subsets), natural-killer cells, monocytes, and B-lymphocytes (including naïve, resting memory and activated memory B-lymphocyte subsets).

These studies led to the conduct of a United States Food and Drug Administration (US FDA) GLP-compliant 4-week repeat-dose IV toxicology study of VIS649 in cynomolgus monkeys, with a 20-week recovery period. Monkeys received weekly VIS649 injections for 4 weeks, at doses of 0 mg/kg (control), 25 mg/kg, 50 mg/kg, or 100 mg/kg.

VIS649-related reductions in total serum IgA levels were observed in all VIS649-treated animals [REDACTED] and the reductions were reversible as trends towards return to baseline were observed at all doses. All 3 dose levels demonstrated maximal pharmacologic effect that were consistent with previous studies in reduction in serum IgA and IgG levels with a minimal effect on IgM levels in VIS649 treated animals in comparison to the controls.

Serum IgG levels were moderately reduced [REDACTED] for a majority of animals at all timepoints. Serum IgM concentrations did not differ significantly between groups, including control animals.

There was no effect of VIS649 on measured plasma cytokine concentrations in the monkey toxicology studies (nor did VIS649 stimulate significant cytokine release in an *in vitro* human peripheral blood lymphocyte cytokine release assay).

To test the effect of VIS649 on de-novo humoral immune responses to a novel (T-cell dependent) antigen challenge, monkeys were vaccinated with keyhole limpet hemocyanin (KLH) at Day 7 during dosing, with measurement of KLH-specific IgG and IgM levels through 21 days post

immunization. The kinetics of IgM and IgG responses were similar between VIS649 treated and control animals, with moderate suppression of KLH-specific IgG levels which was consistent with the non-specific suppression seen in total IgG levels.

Based on results from this pivotal toxicology study, the no-observed-adverse-effect level (NOAEL) was considered to be 100 mg/kg/dose [REDACTED]

[REDACTED]. The 100 mg/kg dose is 5-fold greater than the highest dose (20 mg/kg) permitted in this first-in-human study and 200-fold greater than the lowest dose (0.5 mg/kg) to be administered in this FIH study.

[REDACTED]
[REDACTED]
[REDACTED]
[REDACTED]
[REDACTED]

The relatively selective and reversible effect of VIS649 on serum immunoglobulin levels [REDACTED] with maximal (but not completely suppressive) effect on IgA suggests that APRIL inhibition may be uniquely suited as a therapeutic strategy for IgA nephropathy.

Further details can be found in the IB [2].

1.2. Rationale for the Clinical Study

This first-in-human (FIH) study will assess the safety and tolerability, pharmacokinetics (PK)/pharmacodynamics (PD) of VIS649, a humanized IgG₂ mAb that binds to and blocks the biological actions of the B-cell growth factor, APRIL.

The study is being conducted to establish a dose range that is well tolerated by the majority of study subjects and to provide exploratory data on the potential for the treatment of IgAN, an autoimmune glomerulonephritis characterized by the deposition of IgA-containing immune complexes in the kidney. The results of the clinical study will inform the design and dose selection of subsequent studies.

1.3. Risk-benefit Assessment

While VIS649 has not been evaluated in humans, the known effects of mAbs in humans suggest the following potential toxicities for single dose administration:

1. Infusion reactions: Anaphylaxis, fever, chills, rigors, nausea, vomiting, pain, headache, dizziness, shortness of breath, bronchospasm, hypotension, hypertension, pruritus, rash, urticaria, angioedema, diarrhea, tachycardia, and chest pain
2. Delayed allergic reactions: Serum sickness (i.e., urticaria, fever, general glandular enlargement, joint pains)
3. General: Injection site reaction

Mechanism based potential toxicities that might be anticipated based on VIS649 mechanism of action and preclinical studies include:

IgA suppression risks: VIS649 treatment is expected to reduce human IgA levels, with a predicted maximal reduction (with repeated dosing) to approximately 75% below baseline. In this single-ascending dose study, this degree of suppression is unlikely to be achieved, but it is anticipated that at least in the higher dose cohorts, IgA levels will be reduced below baseline, with effect persisting over weeks.

The normal range for serum IgA is approximately 70 to 400 mg/dL in adults [REDACTED]

[REDACTED]

[REDACTED]

Selective IgA deficiency (defined as persistently undetectable IgA, [REDACTED]) is the most common inherited immunodeficiency syndrome (occurring in about 1 in 500 Caucasian individuals). [3]. While this condition has heretofore been considered generally benign and is asymptomatic in the majority of patients, there is increasing recognition that selective IgA deficiency may be associated with recurrent sinopulmonary infection, allergy, autoimmunity and gastrointestinal microbiome perturbation [4, 5]. The risk for occurrence of these complications in the current study is low for multiple reasons: 1) IgA is expected to be suppressed, but not reduced to undetectable levels, 2) in this single dose-study, the effects on IgA levels are expected to be transient, and 3) the syndrome of selective IgA deficiency is often associated with additional immunologic impairments including T-cell disorders and common variable immunodeficiency syndrome.

IgG suppression risks: VIS649 is expected to have a moderate effect on serum IgG levels (with approximately 40% suppression-below-baseline nadir values predicted).

The normal range for serum IgG is approximately 600 to 1600 mg/dL in adults, [REDACTED]

[REDACTED]

[REDACTED]

In common variable immunodeficiency (CVID), also known as acquired hypogammaglobulinemia, total IgG levels are typically below 250 mg/dL with median values at diagnosis in two recent U.S. cohort studies of 210 mg/dL and 120 mg/dL, respectively [6]. The condition is of heterogenous origin, with loss of function mutations in an APRIL receptor, TACI, identified as one causal association [7]. Proposed diagnostic criteria for CVID include: presence of hypogammaglobulinemia [REDACTED] plus a history of recurrent or chronic infection or autoimmunity and with associated IgA deficiency [REDACTED] or IgM deficiency [REDACTED] [8]. Common variable immunodeficiency is associated with recurrent otitis media, chronic sinusitis, and recurrent pneumonia often resulting in bronchiectasis [9]. Longitudinal studies have demonstrated high rates of lymphoma and diseases of autoimmunity [10]. The risk of these complications in the current study is considered quite low, given the moderate and transient reductions in IgG levels that are anticipated.

Non-specific immunosuppression risks: In preclinical toxicology studies, de-novo humoral immune responses to a novel antigen were not suppressed, and peripheral blood myeloid cell line populations were unaffected. However, there is the possibility of non-specific immunodeficiency with potential risk of exacerbation of pre-existing latent infection or poor response to new infection. These risks are considered minimal due to the single-dose design of this trial, and the expected transient nature of effects.

Pharmacodynamic data including measurement of changes in serum IgG, IgA, and IgM levels in relation to VIS649 exposure will provide valuable information for refinement of the human PK/PD model and selection of appropriate doses for a repeat-dose study. Predicted maximal effects on serum IgG, IgA and IgM levels versus normal range, inclusion criteria thresholds, and stopping rule IG thresholds are summarized in [Table 1](#).

Table 1 Serum Immunoglobulin Normal Ranges, Inclusion Criteria, Predicted Maximal Nadirs, and Stopping Rule Thresholds

Immunoglobulin Class	Serum Concentration Normal Range in Adults ¹	[REDACTED]	[REDACTED]	[REDACTED]
IgA	66-433 mg/dL [0.66-4.33 g/L]	[REDACTED]	[REDACTED]	[REDACTED]
IgG	635-1741 mg/dL [6.35-1.74 g/L]	[REDACTED]	[REDACTED]	[REDACTED]
IgM	45-281 mg/dL [0.45-2.81 g/L]	[REDACTED]	[REDACTED]	[REDACTED] or more patients

¹ Immunoglobulin reference ranges for healthy adult volunteers from the laboratory performing these tests for the study (GenX Lab), as measured with a Beckman Coulter Analyzer, instrument AU480.

[REDACTED]

There will be no direct health benefit for healthy subjects from receipt of the study drug. The protocol has been designed to minimize the risk to research participants. Subjects will be monitored to detect adverse events (AE)s during the study and followed appropriately to ensure resolution of AEs. Sentinel dosing will be employed within each cohort, and available blinded safety data will be assessed after each dose level to determine if it is safe to escalate to the next planned dose.

2. STUDY OBJECTIVES

2.1. Primary Objective

- To evaluate the safety and tolerability of VIS649 in healthy subjects.

2.2. Secondary Objectives

- To characterize the PK profile of VIS649
- To evaluate the effect of race on the pharmacokinetic profile of a single intravenously (IV) dose of VIS649 in healthy Japanese and non-Japanese subjects
- To characterize the levels of anti-drug antibodies
- To characterize the effect of VIS649 on PD parameters including:
 - changes in serum total IgA, IgG and IgM concentrations and time to recovery
 - changes in whole blood circulating lymphocyte populations

3. OVERALL DESIGN AND PLAN OF THE STUDY

3.1. Overview

This is a phase 1, randomized, placebo-controlled, double-blind, single ascending dose study to investigate the safety, tolerability, PK/PD of the IV administration of VIS649 in healthy subjects.

The study will be conducted in four sequential dosing cohorts enrolling nine subjects per cohort, with an optional fifth cohort. Each cohort will have 4 Japanese subjects. Subjects will be randomized to VIS649 or placebo in a ratio of 7:2 (7 active, 2 placebo). No more than one Japanese subject per cohort may be randomized to receive placebo. Safety, PK and PD data from the initial cohorts will be assessed, to determine whether to initiate a fifth dosing cohort at a dose not to exceed 20 mg/kg.

The study comprises of:

- A Screening Visit up to 28 days before dosing
- An in-house stay for approximately 2-3 days, with admission to the study center on Day -1, dosing on Day 1, and discharge in the morning of Day 2
- A post-administration period of 16 weeks
- Outpatient visits, on Day 3 (+1 day), 7 (\pm 1 day), 14, 21, 28, 35, 42, 49, 56, 70, 84 and 98 (all visits \pm 3 days)
- A final Follow-up visit on Day 112 (\pm 3 days); Two additional follow-up visits may occur, at Weeks 20 and 24 post-dosing, if serum immunoglobulins have not returned to $>$ lower limits of normal by the Week 16 (Day 112) visit, or if emerging trial data suggest a value of later follow-up (i.e., for detection of ADA responses).

The total duration of the clinical study per subject will be up to approximately 20 weeks (5 months), including the Screening period with the possibility of duration extending to 28 weeks (7 months) if follow-ups visits are required.

Potential subjects will be carefully screened for eligibility prior to study enrollment. Randomization and blinding will occur according to a core randomization list administered by the site's unblinded pharmacist.

Eligible subjects will report to the Clinical Pharmacology Unit (CPU) at study check-in (Day -1) and will be required to stay in the CPU until Day 2 (24 hours post infusion). On Day 1, a single

dose of VIS649 or placebo will be administered intravenously in the morning after a light meal (as per the clinical unit standard). Pharmacokinetics sampling will occur on Day 1 starting with a collection prior to the start of infusion, end of infusion, and at 2 hours, 8 hours and 24 hours post end of infusion. Pharmacokinetics samples will also be drawn on Days 3, 7, 14, 28, 42, 56, 70, and 112. Pharmacodynamics sampling (serum immunoglobulin levels, lymphocytes and sub Ig types) will occur as outlined in the Schedule of Assessments ([Table 9](#)).

The initial cohort will be dosed with 0.5 mg/kg of VIS649. Escalation to next dosing level (2.0 mg/kg) will occur after review of blinded safety data through Day 14 by the Safety Monitoring Committee (SMC) comprised of the Investigator, an independent Medical Monitor, and the Sponsor. For subsequent cohorts (6.0 mg/kg and 12 mg/kg, and the optional fifth dosing cohort), escalation will occur after review of safety data through Day 28 by the SMC. Assessment of safety will be determined by evaluation of:

- Vital sign measurements
- Physical examinations
- Hematology, chemistry, and urinalysis laboratory testing
- 12-lead electrocardiograms (ECG)
- Adverse events, and
- Serum immunoglobulin levels

Pharmacokinetic data will not be available for dose escalation decision making. Pharmacokinetic data will be reviewed in a blinded fashion after each cohort is available, and may result in a dose adjustment for subsequent cohorts (including optional cohort 5, and none to exceed 20 mg/kg). Any adjustments will be reviewed and approved by the Investigator, Medical Monitor, and the Sponsor.

If dose escalation is stopped based on available blinded safety data, the current dose level will be considered as the minimum intolerable dose (MID). The dose just below the MID will be regarded as the maximum tolerated dose (MTD). If the dose escalation is stopped due to reaching exposure limit without dose limiting safety findings, the MTD will not be determined. Dose de-escalation may occur in additional cohorts, to further refine clinically relevant dose levels.

Stopping rules are described in Section [3.4](#).

Procedures related to the clinical study are detailed in the Schedule of Assessments ([Table 9](#)).

Doses will be administered intravenously to subjects in approximately 4 dose cohorts (see [Table 2](#)). An additional cohort may be enrolled and proceed at a dose not to exceed 20 mg/kg (given the safety coverage described in Section [5.2](#)), if deemed appropriate by the SMC. Cohorts are planned as follows:

Table 2 Cohorts and Dose Administration

Cohorts	Number of Subjects	Treatment
Cohort 1	N=7	VIS649 0.5 mg/kg ¹
	N=2	Placebo
Cohort 2	N=7	VIS649 2.0 mg/kg ²
	N=2	Placebo
Cohort 3	N=7	VIS649 6.0 mg/kg ²
	N=2	Placebo
Cohort 4	N=7	VIS649 12 mg/kg ²
	N=2	Placebo
Optional Cohort 5	N=7	VIS649 TBD, not >20 mg/kg
	N=2	Placebo

[figure not shown]
TBD: To be decided

¹After all subjects have completed assessments through Day 14, blinded safety data will be reviewed and a dose escalation decision for the subsequent cohort will be made by the SMC. If dose escalation is stopped, dose de-escalation may occur in additional cohorts, to further refine clinically relevant dose levels.

² After all subjects have completed assessments through Day 28, blinded safety data will be reviewed and a dose escalation decision for the subsequent cohort will be made by the SMC. If dose escalation is stopped, dose de-escalation may occur in additional cohorts, to further refine clinically relevant dose levels.

Please refer to [Table 9](#) for a detailed list of procedures performed on each study day and visit.

Figure 1 Study Flow Chart – Single Ascending Dose Design

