3.4. Stopping Criteria for the Clinical Study and Dose Escalation Criteria

If any of the dose limiting toxicities listed below are met, the relevant subject(s) data may be unblinded. If the toxicity is present in ≥ 1 subject randomized to active drug, then dose escalation will pause. Depending upon the nature of the event, a decision may be made to resume dosing, to proceed into the next cohort at a lower dose level, or to stop the study.

Based on safety criteria, the dose adjustment/stopping criteria are as follows:

- Adverse event stopping criteria:

- Any AE of severe intensity and related causality
 - Any SAE of related causality
- Vital sign stopping criteria:
 - Symptomatic hypotension (systolic blood pressure [SBP] <85 mmHg). If symptomatic hypotension that is related to the study drug is observed during the study, then a minimum of two repeat BP measurements should be obtained over a brief period. The mean of the three SBP measurements will be used to determine stopping criteria.
 - Tachycardia defined as heart rate >120 beats per minute (bpm) lasting longer than 30 minutes or with impaired consciousness
- Electrocardiogram stopping criteria:
 - QT interval [REDACTED] >500 msec (If a prolonged QTc interval is observed during the study, then a minimum of two repeat ECGs should be obtained over a brief period. The mean of the three ECGs will be used to determine stopping criteria.)
- Clinical laboratory stopping criteria:
 - Alanine aminotransferase (ALT) ≥3 times the upper limit of normal (ULN)
 - Aspartate aminotransferase (AST) ≥3 times the ULN
 - Serum creatinine >1.5 times the ULN
 - A decrease from Baseline in hemoglobin concentration >3 g/dL
 - White blood cell count <1,500/mm³
 - Platelets <50,000/mm³
 - Persistent serum IgA reduction to <15 mg/dL (with at least two measurements over at least one week apart) in ≥2 patients
 - Persistent serum IgA reduction to <7 mg/dL (or below local laboratory limit of detection) (with at least two measurements, at least one week apart) in any single patient
 - Persistent serum IgG reduction to <300 mg/dL (with at least two measurements, at least one week apart) in ≥2 patients
 - Persistent serum IgM reduction to <25 mg/dL (with at least two measurements, at least one week apart) in ≥2 patients.

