6.2.1.5. Follow-up of Adverse Events

All AEs experienced by a subject, irrespective of the suspected causality, will be monitored until the event has resolved, until any abnormal laboratory values have returned to Baseline or stabilized at a level acceptable to the Principal Investigator and Medical Monitor, until there is a satisfactory explanation for the changes observed or until the subject is lost to follow-up.

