6.2.2. Clinical Laboratory Assessments

Samples for clinical laboratory assessments will be collected at the time points detailed in the Schedule of Assessments [Table 9](#). Clinical laboratory tests will be performed by the laboratories mentioned in the List of Study Staff of this clinical study protocol. Samples will be collected in appropriate tubes and handled according to standard procedures of the applicable laboratory.

[Table 7](#) lists the biochemistry, hematology and urinalysis tests that will be performed by the local laboratory for safety blood samples.

Table 7 Clinical Laboratory Assessments

Hematology	
White blood cell (WBC) count	Neutrophils (percentage and absolute count)
Red blood cell (RBC) count	Lymphocytes (percentage and absolute count)
Hemoglobin (Hb)	Monocytes (percentage and absolute count)
Hematocrit (HCT)	Eosinophils (percentage and absolute count)
Mean corpuscular volume (MCV)	Basophils (percentage and absolute count)
Mean corpuscular hemoglobin (MCH)	Platelet count
Mean corpuscular hemoglobin concentration (MCHC)	RBC distribution width
Coagulation	
Prothrombin time (PT)	International Normalized Ratio (INR)
Activated partial thromboplastin time (aPTT)	
Clinical Chemistry	
Alanine aminotransferase (ALT)	Glucose
Albumin	Lactate dehydrogenase (LDH)
Alkaline phosphatase (ALP)	Phosphorus
Aspartate aminotransferase (AST)	Potassium
Blood urea nitrogen (BUN)	Sodium
Calcium	Total bilirubin
Chloride	Total protein
Cholesterol	Triglycerides
Creatinine	Uric acid
Gamma glutamyl transferase (GGT)	
FSH (Screening Visit only; all female subjects)	
Urinalysis	
Bilirubin	Blood
Glucose	pH and specific gravity
Ketones	Protein
Leukocytes	Urobilinogen
Nitrite	
Microscopic (only for abnormal urine stick test findings)	
Viral Serology	
Human immunodeficiency virus (HIV) (Types 1 and 2) antibodies	Hepatitis C virus antibody (anti-HCV)
Hepatitis B surface antigen (HBsAg)	
Urine Drug Screening and Cotinine Test	
Amphetamines	Cocaine
Barbiturates	Opiates
Benzodiazepines	Phencyclidine
Cannabinoids	Cotinine
Urinary creatinine (to exclude dilution effect)	Ethanol
Pregnancy Testing	
Serum/urine human beta chorionic gonadotrophin (women of childbearing potential only)	

Abnormal laboratory results should be recorded as AEs (e.g., Principal Investigator judgment or outside the specific reference range).

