ECG	x	x	X ⁴																
Concomitant Medications	x	x	x		x	x	x	x	x	x	x	x	x	x	x	x	x	x	
AE Check		x	x	x	x	x	x	x	x	x	x	x	x	x	x	x	x	x	
IV Study Infusion			x																
Laboratory Assessments																			
Serum Chemistry / Coagulation	x	x			x		x												
Urinalysis	x	x			x				x			x				x			
Hematology (CBC with differential)	x	x			x		x		x			x		x					
Blood Sampling for PK ⁵			X ⁵	X ⁵	x	x	x		x		x		x	x		x			
Blood Sampling for PD (Immunoglobulins)	x	x			x	x	x	x	x	x	x	x	x	x	x	x	x	x	
Blood Sampling for Ig subtypes		x			x				x			x		x		x			
Blood Sampling for PD (lymphocyte populations)		x			x				x			x		x		x	x	x	

Activity	Screen	Baseline	Post-Dosing Period Assessments															Additional Visits ⁷	
Time Point (Day)	Days -30 to -1	BL D-1 pre-dose	D1	D2	D3	W1/ D7	W2/ D14	W3/ D21	W4/ D28	W5/ D35	W6/ D42	W7/ D49	W8/ D56	W10/ D70	W12/ D84	W14/ D98	W16/ D112	W20	W24
+/- visit allowance	N/A	N/A	N/A	N/A	+1	+/-1	+/-3	+/-3	+/-3	+/-3	+/-3	+/-3	+/-3	+/-3	+/-3	+/-3	+/-5	+/-5	
Blood sampling for ADA			x							x			x			x			

Abbreviations: ADA: Anti-drug Antibody; AE: Adverse event; D: Day; ECG: Electrocardiogram; HBsAG: Hepatitis B surface antigen; HIPAA: Health Insurance Portability and Accountability Act; HIV: Human Immunodeficiency Virus; Ig: Immunoglobulin; IV: Intravenous; N/A: Not Applicable, PD: Pharmacodynamics; PK: Pharmacokinetics; W: Week.

1. The first two subjects of each cohort will be discharged 24 hours (Day 2) after the study infusion. All other subjects are discharged on Day 2, 24 hours after study infusion. Discharge from the Phase 1 unit will not occur prior to performing the 24 h post infusion study procedures.
2. Optional Visit at Week 20 is only to be made if immunoglobulin levels (IgG, IgM, or IgA) have not returned to normal range by Week 16; the Optional Visit at Week 24 is only to be made if immunoglobulin levels have not returned to normal range by Week 20.
3. Vitals signs at Screening will include height and weight, to permit estimated creatinine clearance calculation, as well as blood pressure (bp), heart rate (hr), respiratory rate (rr) and temperature. Vital signs at other timepoints will be limited to bp, hr, and rr. Vital signs measurements on Day 1 will be

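### Low-cost improvement: draw serum chemistry at Day 28 where the Day 28 review leads to a higher dose, since the last scheduled ALT, AST and creatinine values are from Day 14

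*Protocol*

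**What the plan says.** Escalation from cohort 1 follows a review through Day 14. For 6.0 mg/kg, 12 mg/kg and the optional fifth cohort, Protocol Section 3.1 states that "escalation will occur after review of safety data through Day 28 by the SMC". Footnote 2 to Table 2 repeats the rule for cohorts 2 to 4: "After all subjects have completed assessments through Day 28, blinded safety data will be reviewed". The components of the review include "Hematology, chemistry, and urinalysis laboratory testing".

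Section 3.4 sets stopping limits for ALT and AST (at least 3 times the ULN) and for creatinine ("Serum creatinine >1.5 times the ULN"). If a listed toxicity occurs in at least one "subject randomized to active drug, then dose escalation will pause".

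In Protocol Table 9 the row "Serum Chemistry / Coagulation" is marked at Screening, Day -1, Day 3 and Day 14 only. SAP Table 1 has the same four marks.

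For abnormalities already found, Section 6.2.2 says "Abnormal laboratory results should be recorded as AEs", and Section 6.2.1.5 has AEs followed "until any abnormal laboratory values have returned to Baseline or stabilized at a level acceptable to the Principal Investigator", among other end points. Section 6.2.2 also allows extra tests when there is a medical indication.

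**The concern.** The review window for the higher doses is twice as long as for the first cohort, but the added two weeks bring no scheduled value for three of the analytes that can pause escalation. The other laboratory stopping analytes in Section 3.4 are hemoglobin, white cells, platelets, IgA, IgG and IgM. All of these are drawn at Day 28. ALT, AST and creatinine are the only ones that are not.

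The subject at issue has a normal Day 14 chemistry result, then a first rise past a limit without symptoms, still present at Day 28. No scheduled test of the three analytes would show it, and the next cohort would be dosed higher. Follow-up of abnormal values cannot start without an abnormal value, and a silent rise gives no medical indication for an unscheduled test.

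**Working it through.** 1. **Schedule against blood budget.** The chemistry marks in Table 9 are Screening, Day -1, Day 3 and Day 14, which is 4. Table 8 budgets 4 samples of 8.5 mL: 4 × 8.5 = 34 mL, as printed. The column positions up to Day 28 agree with the PK row, whose days are written out in Section 6.3.1 (Days 3, 7, 14, 28). The absence of a Day 28 mark is therefore not an extraction fault.

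2. **What Day 28 does include.** Hematology, urinalysis, immunoglobulins, PK, vital signs and a brief physical examination are marked. Blood is therefore already drawn at this visit.

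3. **Gap from last chemistry to the Day 28 visit.** Both visits have a ±3-day window: Day 11 to 17 and Day 25 to 31.
   - Nominal: 28 − 14 = 14 days
   - Shortest: 25 − 17 = 8 days
   - Longest: 31 − 11 = 20 days

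4. **Decisions affected.** In the protocol as provided, the Day 28 reviews of cohorts 2, 3 and 4 can each lead to a higher dose: 3 decisions, 3 × 7 = 21 active subjects. In the SAP design cohort 5 repeats 6.0 mg/kg, so only the reviews of cohorts 2 and 3 do: 2 decisions, 2 × 7 = 14 active subjects.

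5. **Illustration only.** The documents give no rate for such a rise. Let p be an assumed chance per active subject of a new silent rise past a limit, present at Day 28. The chance of at least one among 7 active subjects is 1 − (1 − p)^7.

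| Assumed p | At least one of 7 |
|---|---|
| 0.1% | 0.7% |
| 1% | 6.8% |
| 5% | 30.2% |

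   The result depends almost entirely on p, which has no source. The table shows how wide the uncertainty is and should carry no weight as evidence of risk.

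6. **Cost of one extra draw.** Chemistry becomes 5 × 8.5 = 42.5 mL and the total 327 + 8.5 = 335.5 mL, a rise of 8.5/327 = 2.6%. Tubes needed: cohorts 2 to 4, 3 × 9 = 27; cohorts 2 and 3, 2 × 9 = 18.

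**The case against.** The strongest reply is that this is a preference, not a fault. The review is cumulative, and naming chemistry as a component does not promise a fresh draw. ECG is on the same list and is last scheduled on Day 1. The longer window also has a use that needs no chemistry: Section 1.3 expects IgA effects to last for weeks, and the immunoglobulin stopping rules need two low values at least a week apart. Subjects are screened on liver and renal tests and receive one dose. Section 5.2 reports no drug-related clinical findings in monkeys up to 100 mg/kg weekly. All of this stands.

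Existing cover also counts. A rise visible by Day 14 would be recorded and followed. Urinalysis at Day 28 includes bilirubin, urobilinogen, protein and blood, but it is an insensitive, indirect signal and does not measure ALT, AST or creatinine. The cover leaves out only the new silent rise.

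An extra draw has a downside as well. The ALT, AST and creatinine limits require neither relatedness nor a confirmatory repeat, unlike the hypotension and QT rules. One isolated value in one active subject could therefore pause escalation for a non-drug reason. This stands, but Section 3.4 allows dosing to resume after review.

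Finally, the SAP follows a later protocol amendment than the protocol provided, and its Section 3.1 describes 6.0 mg/kg as already evaluated in cohort 3. At least the decision to open 6.0 mg/kg may therefore have passed.

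A reader might infer that the protocol fails to deliver data it promised to the SMC, or that the percentages above show a material chance of a missed toxicity. The documents support neither: no Day 28 chemistry draw is promised, and no event rate is given.

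**Conclusion.** The gap is real but narrow. At the Day 28 escalation reviews the newest scheduled ALT, AST and creatinine values are nominally 14 days old (8 to 20 with windows). A new asymptomatic rise after a normal Day 14 result would not be found by any scheduled test of these analytes before the next dose level opens. This bears on up to 3 decisions in the protocol as provided and 2 in the SAP design. Cohort 1 is unaffected, because its Day 14 review has a Day 14 chemistry draw.

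The clinical size of the gap cannot be estimated from the documents. The case for change rests on three things: this is first-in-human escalation, the protocol itself lets one affected active subject pause it, and closing the gap costs very little. It is a worthwhile improvement and not the correction of an error. One draw has limits too: a rise that came and went between Day 14 and Day 28 would still be missed.

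**What to change.** Add serum chemistry, without coagulation, at the existing Day 28 visit in Protocol Table 9 and SAP Table 1, by splitting the combined row or adding a footnote. Apply it to the cohorts whose Day 28 review leads to a higher dose: cohorts 2 to 4 in the protocol as provided, or cohorts 2 and 3 in the SAP design. Have the results available before the SMC meets.

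Update the blood-volume table for those subjects by 8.5 mL, from 327 to about 335.5 mL in the protocol as provided. The total in the amendment that the SAP follows was not available, so the same 8.5 mL should be added to whatever figure it gives.

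The cost is one tube and assay per subject (27 or 18 in all), a schedule amendment, and the small added chance of a non-drug pause. No extra visit is needed. No delay is expected, because Section 6.2.2 assigns chemistry to the same local laboratory as the Day 28 hematology that the review already waits for.
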